## **8. EXTENT OF EXPOSURE AND TREATMENT COMPLIANCE**

### **8.1 Exposure to Investigational product**

A summary table showing number of subjects exposed and number of administrations received will be produced by period, overall and treatment for the Safety Analysis Set.

A listing will be created by subject number and visit giving the date and time of dose administration, for the Safety Analysis Set.

### **8.2 Measurement of Treatment Compliance**

Since this is a Phase 1 study in which the study medication is administered at the Clinical Research Center (CRC), no summary of treatment compliance will be produced.

## **9. PRIOR AND CONCOMITANT MEDICATION**

Version 2016MARDD (Basic) or newer of the WHODRUG will be used to classify prior and concomitant medications by therapeutic class. Medications will also be coded by the Anatomical Therapeutic Chemical (ATC) classification system.

Medications starting before the first dose of investigational product will be considered prior medications. Medications taken during Period 1 and stopping before the first dose of investigational product in Period 2 will be considered concomitant with Period 1. Medications taken after the first dose of investigational product in Period 2 will be considered concomitant with Period 2. If a medication is taken during Period 1 and Period 2 then it will be considered concomitant with both periods.

Both prior and concomitant medication usage will be summarized overall and by the number and proportion of subjects receiving each medication within each level 1 (anatomical main group) ATC group and preferred term for the Safety Analysis Set. Prior medication will be summarized by treatment sequence and concomitant medication will be summarized by treatment. Medications can be counted both as prior and concomitant medication, and concomitant medications can be counted under one or both treatments. Multiple medication usage by a subject in the same category will be counted only once. When calculating the number of subjects receiving medications overall for all treatments combined, each subject will be counted only once even if the medication is taken in both treatment periods.

All prior and concomitant medication will be listed.

A separate listing will be produced for the prior and concomitant medications of interest, which are calcium, vitamin D (any form), and thiazide diuretics.

## **10. EFFICACY ANALYSES**

No efficacy analysis will be performed for this study.

### **10.1 Primary Efficacy Endpoint(s) and Analysis**

Not applicable.

### **10.2 Key Secondary Efficacy Endpoint(s) and Analysis**

Not applicable.

### **10.3 Other Secondary Efficacy Endpoint(s) and Analysis**

Not applicable.

### **10.4 Exploratory Efficacy Endpoint(s) and Analyses**

Not applicable.

## 11. SAFETY ANALYSES

The safety analysis will be performed using the Safety Analysis Set. Safety variables include AEs and TEAEs, clinical episodes of hypocalcemia and/or hypercalcemia, and hypercalciuria, clinical laboratory variables, vital signs, and ECG variables. For clinical laboratory and vital sign variables, the last value collected before the first dose of investigational product in that period will be used as baseline for all analyses of that safety variable in that period.

Assessments at the follow-up visit will be assigned to the last treatment the patient received. Early termination visits will be summarized separately, and assigned to the treatment in Period 1 if prior to first dose of investigational product in Period 2, and assigned to treatment in Period 2 if after the first dose of investigational product in Period 2.

For handling of unscheduled visits, refer to Section 18.

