**Table 1 Schedule of Assessments**

Study Visit	Screening		Predose Assessment		Treatment Period 1		Washout	Predose Assessment		Treatment Period 2		Follow-up
	Admin.	Clinical	TP1, D-2	TP1, D-1	TP1, D1	TP1, D2	W a,b	TP2, D-2	TP2, D-1	TP2, D1	TP2, D2	FU
Study Relative Day/ Study Procedures	-120 to -03	-28 to -03	-2	-1	1	2		-2	-1	1	2	Follow-up c
Alcohol breath test screening			X					X				
Urine collection container provided to subject		X p										
IP administration					X					X		
PK blood sampling j					X	X				X	X	
PD blood sampling j				X	X	X			X	X	X	
PD urine (continuous collection) j				X	X	X			X	X	X	
Check-in to CRC			X					X				
24-hour urine collection obtained		X q										
In-house confinement				X	X	X			X	X	X	
Discharge from CRC (after last assessment)						X					X	
Adverse events/serious adverse events f	X r	X	X	X	X	X	X	X	X	X	X	X
Concomitant medication f		X	X	X	X	X	X	X	X	X	X	X
Administration of usual supplemental oral calcium and active vitamin D		X	X	X			X	X	X			X

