### 7.2.4 Follow-up Period

The follow-up period for this protocol is  $30 \pm 2$  days after the last dose of investigational product. At the end of this period there will be a follow up visit to obtain a blood sample for clinical safety labs, a blood sample for anti-PTH antibodies, query for SAEs, AEs, and concomitant treatments. All AEs and SAEs that are not resolved at the time of this contact will be followed to closure (see Section [8.1](#)).

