**Table 2: Schedule of Assessments**

Study Visit	Screening		Predose Assessment		Treatment Period 1		Washout	Predose Assessment		Treatment Period 2		Follow-up
	Admin.	Clinical	TP1, D-2	TP1, D-1	TP1, D1	TP1, D2	W a,b	TP2, D-2	TP2, D-1	TP2, D1	TP2, D2	FU
Study Relative Day/ Study Procedures	-120 to -03	-28 to -03	-2	-1	1	2		-2	-1	1	2	Follow-up c
medication t												
Administration of usual supplemental oral calcium and active vitamin D		X	X	X			X	X	X			X
Withhold supplemental oral calcium and active vitamin D s					X t					X t		
Administration of supplemental oral calcium only (no active vitamin D) u					X v					X v		

a Washout period should be ≥5 days (ie, 120 hours) and ≤30 days between first dose of each treatment period (whether dosing regimen is BID or QD).

b The investigator may elect to keep the subject in-clinic for the duration of the study, if the washout period is short (eg, 120-172 hours) and/or there are any safety concerns, and provided that there is a minimum washout of ≥120 hours between administration of IP in each treatment period.

c A follow-up visit must be completed 30±2 days after the last dose of IP.

d If applicable.

e Review and update medical history and re-confirm eligibility.

f In the event a subject is prematurely discontinued from the study, every attempt should be made to complete these assessments.

g The safety blood and urine assessments (Period 1 and Period 2), pregnancy test (for all females, Period 2), physical exam (Period 2), and weight (Period 2) should be collected after the scheduled serial PK and PD assessments have been completed on this study day, and prior to discharging the subject from the Clinical Research Center.

h Randomization will occur prior to administration of IP at Treatment Period 1, Day 1 only after all eligibility criteria have been confirmed/re-confirmed.

i Vital sign measurements should be collected in the supine position at each time point.

j See **Error! Not a valid bookmark self-reference.**, Table 3, and Table 4 for detailed collection time points.

k Weight measurement only.

l ECGs will be performed in triplicate measurement at each time point.

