### 11.1 Adverse Events

Adverse events will be coded using Version 19.0 or newer of MedDRA.

An AE (classified by preferred term) that occurs during the study will be considered a TEAE if it has a start date/time on or after the first dose of investigational product or if it has a start date before the date of the first dose of investigational product, but increases in severity on or after the date/time of the first dose of investigational product. If more than 1 AE with the same preferred term is reported before the date of the first dose of investigational product, then the AE with the greatest severity will be used as the benchmark for comparison to the AEs occurring during the study under the preferred term. An AE that occurs more than 5 days (120 hours) after the last dose of investigational product will not be counted as a TEAE.

Adverse events will be assigned to a treatment as follows. If the onset date of the AE is after first dose in Period 1, but prior to first dose in Period 2, and is  $\leq 5$  days after the date of last dose in Period 1 it will be counted as a Period 1 AE. If the onset date of the AE is after first dose in Period 2, and is  $\leq 5$  days after the date of last dose in Period 2 it will be counted as a Period 2 AE. Period 1 AEs will be assigned to the treatment received in Period 1, and Period 2 AEs will be assigned to the treatment received in Period 2. AEs with onset date  $> 5$  days after the last dose in Period 1 and prior to the first dose in Period 2 will be counted as a Washout AE, not assigned to a treatment, and not considered a TEAE. AEs with onset date  $> 5$  days after the last dose in Period 2 will be counted as a Follow-up AE, not assigned to a treatment, and not considered a TEAE.

When summarizing non-TEAEs by treatment, AEs occurring prior to first dose in Period 1 will be excluded, and other non-TEAEs will be assigned to the last treatment received.

An overall summary of the number of subjects with AEs will be presented by treatment and overall, including the number and percentage of subjects with any AEs, serious AEs, AEs related to investigational product, AEs leading to discontinuation of investigational product, severe AEs, and deaths. The number and percentage of subjects with TEAEs and non-TEAEs will be presented for the same categories.

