## 11.2 Clinical Laboratory Variables

Descriptive statistics for clinical laboratory values (in SI units) and changes from baseline at each assessment time point as well as shift tables from baseline to each visit for quantitative variables will be presented by treatment for the following clinical laboratory variables.

**Hematology** Hemoglobin, hematocrit, red blood cells (RBC), platelet count, white blood cell count – total and differential (WBC), total neutrophils, lymphocytes, monocytes, eosinophils, basophils.

**Biochemistry** Sodium, potassium, glucose, blood urea nitrogen, creatinine, calcium, chloride, thyroid stimulating hormone (TSH)a, thyroxine (T4 total)a, triiodothyronine (T3)a, 25(OH)Da, phosphorus, total protein, total CO2 (Bicarbonate), albumin, aspartate transaminase, alanine transaminase, gamma glutamyl transferase, alkaline phosphatase, total bilirubin, uric acid, Creatinine clearancea, β-HCGb, FSHb, Magnesium.

β-HCG=beta-human chorionic gonadotropin; FSH=follicle stimulating hormone; T3=triiodothyronine; TSH=thyroid stimulating hormone

a Tests done at Screening only and therefore will not appear in summary tables. They will be listed.

b Females only.

**Urinalysis** Glucose, specific gravity, blood, ketones, protein, calcium, bilirubin, pH, leukocyte esterase, and nitrites.

Clinical laboratory test values are potentially clinically important (PCI) if they meet either the low or high PCI criteria listed in Table 5. The number and percentage of subjects with post-baseline PCI values will be tabulated by treatment. The percentages will be calculated relative to the number of subjects with available baseline values and at least 1 post-baseline assessment. The numerator is the total number of subjects with at least 1 post-baseline PCI value. A supportive listing of subjects with post-baseline PCI values will be provided for all results for the parameter with a PCI value for a subject, including the subject number, site, baseline, and post-baseline values.

	Parameter	Unit	Lower Limit	Upper Limit
Chemistry	Albumin	g/L	<=20	>=90
	Alkaline Phosphatase	U/L	NA	>2*ULN
	ALT	U/L	NA	>3*ULN
	AST	U/L	NA	>3*ULN
	Bilirubin	µmol/L	NA	>2*ULN
	BUN	mmol/L	NA	>=10.7
	Chloride	mmol/L	<=80	>=125
	Creatinine	µmol/L	NA	>=177
	Glucose	mmol/L	<=1.7	>=13.9
	Gamma glutamyl transferase	U/L	NA	>=100

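### By-treatment lab PCI percentages include samples taken about 30 days after the last dose, because SAP 11 and 11.2 set no time window

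*SAP*

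**What the plan says.** - **Attribution of follow-up data.** SAP 11: "Assessments at the follow-up visit will be assigned to the last treatment the patient received". The sentence covers all follow-up assessments and gives no limit in days.
- **Timing and content of follow-up.** SAP schedule of assessments, footnote c: "A follow-up visit must be completed 30±2 days after the last dose of IP". Protocol 7.2.4: "there will be a follow up visit to obtain a blood sample for clinical safety labs". The schedule marks biochemistry, hematology and urinalysis at this visit.
- **Background treatment at follow-up.** In Protocol Table 1 the row "Administration of usual supplemental oral calcium and active vitamin D" is marked at follow-up.
- **Lab PCI count.** SAP 11.2 tabulates PCI values by treatment: "The numerator is the total number of subjects with at least 1 post-baseline PCI value". SAP 18.3 adds unscheduled values to the count.
- **Table layout.** In SAP 20 the lab PCI tables for hematology (4.6.3) and biochemistry (4.6.6) are titled by treatment only. The vital-sign and ECG PCI tables (4.7.2, 4.8.4) are titled by timepoint and treatment.
- **Adverse events.** SAP 11.1: "An AE that occurs more than 5 days (120 hours) after the last dose of investigational product will not be counted as a TEAE". An event starting more than 5 days after the last Period 2 dose "will be counted as a Follow-up AE, not assigned to a treatment, and not considered a TEAE". For by-treatment summaries of non-TEAEs, however, the same section says that "other non-TEAEs will be assigned to the last treatment received".

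**The concern.** The secondary objective is safety and tolerability, and the lab PCI percentages are one of its by-regimen summaries. Followed as written, a phosphate, magnesium or hematology value outside limits four weeks after dosing, on conventional therapy, is reported as a post-dose finding of whichever regimen the subject received last. For an adverse event with onset that late, the SAP declines to call it treatment-emergent and keeps it out of the TEAE tables. The lab PCI tables have no equivalent separate category, so a reader of Tables 4.6.3 and 4.6.6 cannot tell a Day 2 finding from a follow-up finding. The percentage also depends on how many times each regimen was looked at.

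**Working it through.** **1. Number of safety labs per subject.** Protocol Table 6 gives 6 biochemistry samples: 1 screening + 2 baseline (Day -2 of each period) + 1 QD + 1 BID + 1 follow-up = 6, and 6 × 6 mL = 36 mL. Both figures agree with the table. Period 2 Day -2 is listed as a baseline, so each regimen has one scheduled post-dose lab (Day 2) and the single follow-up lab is added to the regimen given last.

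**2. Distance from the AE window.** Follow-up falls 28 to 32 days after the last dose. Against the 5-day limit that is 28 − 5 = 23 to 32 − 5 = 27 days late.

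**3. Off-drug share at planned numbers (4:4 sequences, all completing).**
- A, C, D, F (n=8 each): 8 Day 2 sets + 4 follow-up sets; 4/12 = 1/3.
- B, E (n=16 each, over two cohorts): 16 + 8; 8/24 = 1/3.

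**4. Effect on the percentage.** The documents give no PCI rates, so q, the probability of a PCI value at a visit, is an assumption, taken as equal at Day 2 and follow-up. With independent visits, the rate is q when a regimen is given first and 1 − (1 − q)² when given second. The pooled 4:4 figure is the mean of the two, and its ratio to q is (3 − q)/2.

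| Assumed q | Given first | Given second | Pooled at 4:4 | Ratio |
|---|---|---|---|---|
| 2% | 2.0% | 3.96% | 2.98% | 1.49 |
| 5% | 5.0% | 9.75% | 7.38% | 1.48 |
| 10% | 10.0% | 19.0% | 14.5% | 1.45 |

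At the other extreme, if a subject who is PCI at one visit is always PCI at the other, the second look adds nobody and the ratio is 1.0.

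**5. When it differs between regimens.** At 4:4 each regimen is second in half the cohort, so both receive the same inflation under this model. With 5:3 sequences, q = 5% and independent visits:
- regimen second in 5 of 8: (3 × 5% + 5 × 9.75%)/8 = 8.0%
- regimen second in 3 of 8: (5 × 5% + 3 × 9.75%)/8 = 6.8%

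**6. Granularity.** One follow-up excursion in a subject with no Day 2 excursion moves a cell of 8 by 1/8 = 12.5 percentage points.

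**7. Which tables are reached.** The only urine criterion in the SAP 11.2 PCI list is 24-hour calcium, and no 24-hour collection is scheduled at follow-up. The list as supplied has no serum calcium row. The effect is therefore shown for Tables 4.6.3 and 4.6.6 only.

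**The case against.** Several points on the other side stand.

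- **Regimen comparison.** A reader might infer that the rule biases the QD against BID comparison. The planned design does not support that: 4:4 sequences balance the effect within each cohort. Imbalance would have to come from cohort expansion, dropout or exclusions.
- **Contradictory windows.** A reader might also infer that SAP 11 and SAP 11.1 use incompatible attribution windows. That is too strong. The 5-day limit defines treatment emergence for AE onset, the SAP never says it governs labs, and 11.1 itself sends late non-TEAEs to the last treatment in separate tables. What the lab PCI tables lack is that separation.
- **Calcium results.** It is tempting to extend the point to urinalysis Table 4.6.10 or to calcium PCI counts. The criteria and schedule do not show any effect there.
- **First regimen.** It would be wrong to say that the regimen given first can never collect follow-up values. For a subject who stops after Period 1, they go to the Period 1 treatment. Early-termination visits before the Period 2 dose go there too, with no 5-day limit, although they are summarized separately.
- **Visibility elsewhere.** Descriptive lab values are by time point, shifts are by visit, and a listing supports the PCI table. A reader can trace an excursion to follow-up, but none of this corrects the PCI percentage itself.
- **Layout.** That the lab PCI tables lack a timepoint rests on their titles; SAP 1 places table specifications in a separate document. The vital-sign and ECG text uses a similar numerator, yet those tables are titled by timepoint. The final lab layout could differ, but the SAP text does not require it.
- **Size.** The ratio near 1.5 needs independent visits, and persistent abnormalities push it toward 1.0. The assumed rates may be too high for some analytes: entry requires creatinine below 133 µmol/L and the PCI limit is 177 µmol/L or above.

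**Conclusion.** The point holds for lab PCI Tables 4.6.3 and 4.6.6. As written, values taken 23 to 27 days beyond the SAP's own treatment-emergence limit enter the regimen percentages, and at planned numbers they make up one third of the scheduled post-baseline lab sets under every treatment. The consequence is inflation by a factor of 1.0 to about 1.5, depending on within-subject correlation and assuming equal PCI probability at Day 2 and follow-up. A different off-drug rate would change that range. The effect is about equal for both regimens of a cohort at 4:4 and differential only if sequences become unequal (8.0% against 6.8% in the 5:3 illustration). The vital-sign and ECG PCI tables, being by timepoint, are not shown to be affected. The study is descriptive and the primary PK and PD analyses are untouched. It is nevertheless worth correcting before database lock, because the misattribution is avoidable at almost no cost.

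**What to change.** 1. **SAP 11 and 11.2.** Restrict by-treatment lab PCI counts to values from the first dose of a period to 5 days after that period's last dose, and before the next period's baseline sample. The second limit is needed because, with the minimum 5-day interval between first doses and no Day 0, Period 2 Day -2 can fall 5 − 2 = 3 days after the first Period 1 dose. Apply the same window to early-termination and unscheduled labs.
2. **Tables 4.6.3 and 4.6.6.** Show follow-up PCI values in a separate follow-up row or column over all subjects. The SAP already reports anti-PTH antibodies overall by timepoint.
3. **SAP 11.1.** Reconcile the two statements on late adverse events, which are left unassigned in one sentence and given to the last treatment in another. State the rule for the by-treatment non-TEAE tables and for Table 4.5.3, which combines TEAEs and non-TEAEs of special interest by treatment.

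The cost is SAP wording and one extra row or column, with no new data. By-treatment PCI percentages may be slightly lower.

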### 11.1 Adverse Events

Adverse events will be coded using Version 19.0 or newer of MedDRA.

An AE (classified by preferred term) that occurs during the study will be considered a TEAE if it has a start date/time on or after the first dose of investigational product or if it has a start date before the date of the first dose of investigational product, but increases in severity on or after the date/time of the first dose of investigational product. If more than 1 AE with the same preferred term is reported before the date of the first dose of investigational product, then the AE with the greatest severity will be used as the benchmark for comparison to the AEs occurring during the study under the preferred term. An AE that occurs more than 5 days (120 hours) after the last dose of investigational product will not be counted as a TEAE.

Adverse events will be assigned to a treatment as follows. If the onset date of the AE is after first dose in Period 1, but prior to first dose in Period 2, and is  $\leq 5$  days after the date of last dose in Period 1 it will be counted as a Period 1 AE. If the onset date of the AE is after first dose in Period 2, and is  $\leq 5$  days after the date of last dose in Period 2 it will be counted as a Period 2 AE. Period 1 AEs will be assigned to the treatment received in Period 1, and Period 2 AEs will be assigned to the treatment received in Period 2. AEs with onset date  $> 5$  days after the last dose in Period 1 and prior to the first dose in Period 2 will be counted as a Washout AE, not assigned to a treatment, and not considered a TEAE. AEs with onset date  $> 5$  days after the last dose in Period 2 will be counted as a Follow-up AE, not assigned to a treatment, and not considered a TEAE.

When summarizing non-TEAEs by treatment, AEs occurring prior to first dose in Period 1 will be excluded, and other non-TEAEs will be assigned to the last treatment received.

An overall summary of the number of subjects with AEs will be presented by treatment and overall, including the number and percentage of subjects with any AEs, serious AEs, AEs related to investigational product, AEs leading to discontinuation of investigational product, severe AEs, and deaths. The number and percentage of subjects with TEAEs and non-TEAEs will be presented for the same categories.

The number and percentage of subjects reporting TEAEs for each treatment will be tabulated by system organ class (SOC) and preferred term; by SOC, preferred term, and maximum severity. TEAEs considered related to investigational product will also be summarized by SOC and preferred term. If more than 1 AE occurs with the same preferred term for the same subject, then the subject will be counted only once for that preferred term using the most severe and most related occurrence for the summarization by severity and by relationship to investigational product. Severe TEAEs, Serious TEAEs and TEAEs leading to discontinuation of investigational product will be summarized by SOC, preferred term and treatment.

A summary table of TEAEs of special interest will be produced showing the number and percentage of subjects reporting TEAEs of special interest for each treatment tabulated by preferred term. The TEAEs of special interest are hypercalcemia, hypocalcemia and hypercalciuria.

The above summaries will be repeated for non-TEAEs. A separate summary of all AEs of special interest (including TEAEs and non-TEAEs) will also be produced.

Listings will be produced for all AEs (including pre-treatment AEs), SAEs, AEs considered related to investigational product, AEs leading to discontinuation of investigational product, deaths, and AEs of special interest.

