#### 8.1.1 Severity Categorization

The severity of AEs must be recorded during the course of the event including the start and stop dates for each change in severity. An event that changes in severity should be captured as a new event. Worsening of pre-treatment events, after initiation of investigational product, must be recorded as new AEs (for example, if a subject experiences mild intermittent dyspepsia prior to dosing of investigational product, but the dyspepsia becomes severe and more frequent after first dose of investigational product has been administered, a new AE of severe dyspepsia [with the appropriate date of onset] is recorded on the appropriate CRF).

The medical assessment of severity is determined by using the following definitions:

**Mild:** A type of AE that is usually transient and may require only minimal treatment or therapeutic intervention. The event does not generally interfere with usual activities of daily living.

**Moderate:** A type of AE that is usually alleviated with specific therapeutic intervention. The event interferes with usual activities of daily living, causing discomfort but poses no significant or permanent risk of harm to the research subject.

**Severe:** A type of AE that interrupts usual activities of daily living, or significantly affects clinical status, or may require intensive therapeutic intervention.

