### **8.2.5 Serious Adverse Event Onset and Resolution Dates**

The onset date of the SAE is defined as the date the event meets serious criteria. The resolution date is the date the event no longer meets serious criteria, the date the symptoms resolve, or the event is considered chronic. In the case of hospitalizations, the hospital admission and discharge dates are considered the onset and resolution dates, respectively.

In addition, any signs or symptoms experienced by the subject after signing the informed consent form, or leading up to the onset date of the SAE, or following the resolution date of the SAE, must be recorded as an AE, if appropriate.

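### A Period 1 adverse event that only eases after the Period 2 dose is also counted as treatment-emergent under the Period 2 regimen

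*SAP*

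**What the plan says.** Protocol 8.1.1 sets how AEs are recorded: "The severity of AEs must be recorded during the course of the event including the start and stop dates for each change in severity", and "An event that changes in severity should be captured as a new event". Neither sentence is limited to worsening. A further sentence covers the upward case for events that precede treatment: "Worsening of pre-treatment events, after initiation of investigational product, must be recorded as new AEs".

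SAP 11.1 sets how those records are classified. An AE "will be considered a TEAE if it has a start date/time on or after the first dose of investigational product"; this clause has no severity condition. An alternative clause, joined by *or*, admits an AE with an earlier start if it "increases in severity on or after the date/time of the first dose of investigational product". Where more than one AE of a preferred term precedes the first dose, "the AE with the greatest severity will be used as the benchmark for comparison to the AEs occurring during the study".

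The period then follows from the onset date. An AE belongs to Period 1 if it begins after the first Period 1 dose, before the first Period 2 dose, and no more than 5 days after the last Period 1 dose. It belongs to Period 2 if it begins after the first Period 2 dose and no more than 5 days after the last one. Finally, "Period 2 AEs will be assigned to the treatment received in Period 2". Nothing in the section ties a record to an earlier record of the same episode.

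**The concern.** The two documents use different units. The protocol's record is a stretch of constant severity; the SAP treats each record as an event with its own onset. A step down in severity therefore looks like a new onset, and if it falls after the Period 2 dose it is charged to the Period 2 regimen. A sign of recovery from a Period 1 event then appears as harm from the other treatment.

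This bears on the secondary objective, safety and tolerability, which is reported mainly as percentages of subjects with TEAEs by treatment. The SAP's TEAEs of special interest (hypercalcemia, hypocalcemia, hypercalciuria) are tabulated the same way. In a crossover the same subjects supply both columns, so an event entered twice blurs the contrast between regimens that the tables exist to show. SAP section 11 resets the baseline in each period for laboratory values and vital signs, and SAP 11.4 does so for ECGs. AEs have no equivalent.

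**Working it through.** The plan has no figure to reproduce, so the check applies the written rule to records split as the protocol requires.

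**Inputs**
- A new record at each severity change (Protocol 8.1.1).
- The TEAE and period rules of SAP 11.1.
- At least 120 hours between the first doses of the two periods (Protocol 3.1 and Table 1); the second twice-daily dose comes 12 hours after the first.
- At least 8 subjects per cohort (SAP 2.5); Treatments B and E are each given in two cohorts (SAP Table 1).

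**Timeline.** Assume the twice-daily regimen first and the minimum interval. With hour 0 as the first Period 1 dose, the last Period 1 dose is at hour 12 and the single Period 2 dose at hour 120. The gap between those last two is 120 − 12 = 108 hours, or 4.5 days. The event times below are illustrative.

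| Case | Records (start hour, severity) | Literal result |
|---|---|---|
| 1. Period 1 event eases after Period 2 dose | 6 severe; 126 mild | TEAE in Period 1, and TEAE in Period 2 (126 − 120 = 6 h, inside the 120 h window) |
| 2. Period 1 event continues unchanged | 6 mild | Period 1 only |
| 3. Period 1 event worsens after Period 2 dose | 6 mild; 126 moderate | Both periods; the Period 2 entry is defensible |
| 4. Event eases within Period 1 | 6 moderate; 30 mild | Both records in Period 1; subject counted once for the term |
| 5. Event predates dosing, eases after it | −48 moderate; 6 mild | Start-date clause: Period 1 TEAE. Benchmark sentence: suggests not |
| 6. Event predates dosing, worsens after it | −48 mild; 6 severe | Period 1 TEAE, rightly |

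**Case 1** is the error. The start-date clause admits the mild record, the onset date places it in Period 2, and the benchmark cannot remove it because it considers only AEs before the first dose of the study.

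**Case 5** is an ambiguity. The date clause and the benchmark point in opposite directions, and the benchmark is written for more than one prior AE whereas here there is one.

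**Size of one extra subject in a preferred-term row**
- Treatments A, C, D, F: 1/8 = 12.5 points.
- Treatments B, E (8 + 8 = 16 subjects): 1/16 = 6.25 points.

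Both are upper values. SAP 11.1 counts a subject once per preferred term, so the extra record adds nothing if the subject already has that term under that treatment. The cohort sizes are also minimums.

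**With severity records linked as proposed below**, case 1 is a TEAE of Period 1 only, case 5 is not a TEAE, and subject counts in cases 2, 3, 4 and 6 do not change.

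**The case against.** The best defence is that SAP 11.1 classifies AEs by preferred term and compares post-dose AEs with pre-dose severity. If the start-date clause alone decided, the severity clause and the benchmark would have almost no work to do, since the protocol already makes every worsening a new record. This argument stands for events that predate the study's first dose. A reader might infer that such an easing event is certainly miscounted; the text supports only ambiguity. Such an event would in any case be a false TEAE, not one given to the wrong treatment.

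The defence does not reach Period 2. The comparison is anchored to the first dose of the study, and the once-per-term rule itself speaks of several AEs of one term in one subject, so the SAP does treat records as separate AEs. Because the tables are by treatment, that rule does not stop one episode from appearing under both.

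Other strong readings also fail:
- Period 1 events are not moved to Period 2. The original record stays, and the fault is an extra count. Unchanged events are unaffected, and step-downs before the Period 2 dose remain Period 1 or washout AEs.
- Protocol 8.2.5 dates an SAE from when it meets serious criteria, so one might infer that a late-turning event drops out of the safety report. It does not: SAP Table 4.4.2 reports serious non-TEAEs by treatment, Listing 7.2 shows all SAEs, and earlier symptoms are to be recorded as an AE where appropriate.
- Extra records would inflate the event counts mentioned in Protocol 9.9, but SAP 11.1 specifies counts of subjects.

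It is also fair that the study is descriptive, that all AEs are listed individually, and that a special-interest table combining TEAEs and non-TEAEs is planned. The listings let a reader trace an individual case. They do not correct the by-treatment percentages.

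**Conclusion.** The point holds for events that cross from Period 1 into Period 2. Read literally, SAP 11.1 counts a step down in severity after the first Period 2 dose, within the 5-day window, as a TEAE of the Period 2 regimen, and no other rule in SAP section 11 prevents it. This is a stated rule that gives a wrong by-treatment count, not merely a missing detail. For events that predate the first dose of the study and then ease, the SAP needs clarifying because its own sentences disagree.

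One affected subject shifts a preferred-term incidence by up to 12.5 points (n=8) or 6.25 points (n=16), on three conditions: the minimum cohort sizes, sites recording AEs as Protocol 8.1.1 instructs, and no other TEAE of that term in that subject under that treatment. How often an event lasts into Period 2 and then eases is not given and cannot be derived from the documents. The long end of the permitted interval (30 days) leaves more time for events to resolve first. The change is worth making because the denominators are small and the correction is cheap.

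**What to change.** Amend SAP 11.1 as follows:

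1. Within a subject, link contiguous severity records of the same preferred term into one episode.
2. Use the episode's original onset for period assignment.
3. Count a later record of the episode as a TEAE of a period only if its severity exceeds that of the episode ongoing at that period's first dose.
4. State that this comparison governs the start-date clause, including when there is only one prior AE.
5. Where an incomplete stop date prevents linking, keep the record as a separate event (SAP 18.6 does not impute AE stop dates).

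The cost is SAP wording and one derivation step in the AE dataset. The protocol already requires the dates and severities, so no study procedure changes. A few records will not be linkable, and two distinct but adjoining events of the same term could occasionally be joined. Genuine worsening in either period is still counted.
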